This is a multi-site, cluster-randomized clinical trial supported by the infrastructure of the Palliative Care Research Cooperative Group (PCRC). It is a parallel randomization trial with a wait-list control, randomizing nephrologists within each site to receive the intervention at study initiation or after study completion. We will enroll a total of 320 pre-dialysis patients with an estimated glomerular filtration rate (eGFR) of less than 20mL/min/1.73M² who are age 60 and older and have an estimated survival of 18 months or less.³⁶ We expect eight sites are required to ensure complete enrollment (one enrollment plan for example, 8 sites x 4 nephrologists per site with 10 patients per nephrologist = 320). (Note: two sites were added in 2022, for a total of ten sites.) We will follow patients for up to two years after study enrollment. At the start of the study, within each site, nephrologists are randomized to the control or intervention group in a ratio of 1:1. A block randomization scheme will be utilized with blinded block size. Nephrologists assigned to the intervention group will receive training on how to use the Best Case/Worst Case communication tool. Patients in the control group will receive usual care; patients in the intervention group will receive care from their nephrologist trained to use the Best Case/Worst Case communication tool. Palliative care will be available to all patients.

Table: Outcomes Measures for Each Aim				
Construct	Specific Measure	Type; range	Source	Timing
Aim 1: receipt of palliative care and intensity of treatments received at the end of life				
Receipt of palliative care	Any palliative care consult within 12 months of enrollment	Binary; 0/1	Chart review	T0 to 12 mo
Intensity of treatment	ICU admission within 30 days of death	Binary; 0/1	Chart review	T3 minus 30d.
Aim 2: Health-related Quality of Life				
Health related quality of life	Functional Assessment of Chronic Illness Therapy-Palliative Care Version 4 (FACIT-Pal)	Continuous; 0-184	Patient	T2a.... T2h
Aim 3: Quality of Communication				
Quality of Communication	Quality of Communication Questionnaire (QOC)	Continuous; 0-10	Patient	T1
Secondary Outcomes and Follow-up Measures				
Receipt of palliative care	Receipt of any palliative care during study period Hospice enrollment New documentation of advance care planning	Binary; 0/1 Binary; 0/1 Binary; 0/1	Chart review Chart review Chart review	T0 to 2 yr. T0 to 2 yr. T0 to 2 yr.

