Data and Safety Monitoring Plan

No formal interim analyses are planned during this study, and all study outcomes will be assessed at the completion of study follow-up.

Meetings of the DSMB will be held at least two times a year at the call of the Chairperson. DSMB interim report templates will be prepared by a study statistician with assistance from the PCRC and the Data, Informatics and Statistics Core (DISC), to be reviewed by the DSMB members at the first meeting.

Analysis of Primary Outcome

The sample size estimate, 320 patients (160/group), is based on the primary hypothesis that patients in the intervention arm will be more likely to receive palliative care and will have fewer intensive treatments at the end of life. We aim to recruit 32 nephrologists, each treating on average 10 study patients. We estimate a 10% attrition rate for study participation and that 80% of patients will die during the 2-year study period. This study is powered to detect a 10-15% absolute difference in the care patients receive, consistent with other interventions designed to effectively increase access to palliative care.³⁷⁻⁴⁰

Smaller differences are unlikely to be considered meaningful to clinicians, patients or researchers.⁴¹ We desire a two-sided type I error rate of 0.05 and estimate that the between-physician variance is around 10%. We plan to use fixed effects to account for clustering by site because it is faithful to our study design and controls for confounding related to imperfect randomization due to site imbalances better than a random effects model. Assuming the baseline rate of palliative care is 10%,^{42,43} we will have a power of 90% to detect a 14.7% increase and a power of 80% to detect a 12.9% increase in the rate of palliative care received.

General Analysis Plan

Primary Outcome

1. For receipt of **palliative care consult within 12 months of study enrollment**, for each treatment arm, we will report the sample counts and percentages. The denominator for each proportion will include all randomized subjects to the respective treatment arm. The treatment effect will be assessed using a Likelihood Ratio Test (LRT) of the fixed effect from the proportional odds cumulative incidence model, incorporating the competing risk of death.⁴⁴ The model will include a random-intercept for physician, and will include fixed effects for: site, comorbidity, and baseline functional status.

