Alternative Hypothesis: After accounting for baseline differences, there is a difference in the proportion of patients with an ICU admissions within 30 days of death between control patients and Best Case/Worst Case intervention patients.

3. For the **FACIT-Pal total score patient reported health related quality of life** (score range 0-184, 46 items, survey questions 1-46), for each treatment arm, we will report the mean and standard deviation of the **FACIT-Pal total score at last follow-up** (either 2 years of follow-up or last administered survey prior to death, whichever occurs first). The treatment effect will be assessed using a LRT of the fixed effect from the linear mixed-effects model. The linear mixed-effects model will include a random-intercept for physician, and will include fixed effects for: baseline FACIT-Pal total score, site, comorbidity, and baseline functional status.

Null Hypothesis: After accounting for baseline differences, there is no difference in the average FACIT-Pal total score at last follow-up between control patients and Best Case/Worst Case intervention patients.

Alternative Hypothesis: After accounting for baseline differences, there is a difference in the average FACIT-Pal total score at last follow-up between control patients and Best Case/Worst Case intervention patients.

4. For the **FACIT-Pal total score patient reported healthy quality of life** (score range 0-184, 46 items, survey questions 1-46), for each treatment arm, we will report the mean and standard deviation of the **score slopes** (difference in baseline and either 2 years of follow-up or last administered survey prior to death, whichever occurs first, divided by the length of follow-up). The treatment effect will be assessed using a LRT of the fixed effects from the linear mixed-effects model. The linear mixed-effects model will include a random-intercept for physician, and will include fixed effects for: site, comorbidity, and baseline functional status.

Null Hypothesis: After adjusting for baseline differences, there is no difference in the slope of the FACIT-Pal total score between control patients and Best Case/Worst Case intervention patients.

Alternative Hypothesis: After adjusting for baseline differences, there is a difference in the slope of the FACIT-Pal total score between control patients and Best Case/Worst Case intervention patients.

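### The likelihood ratio test of a between-nephrologist effect names no small-sample reference; run in its usual form it exceeds the desired 0.05 whenever physician variance is not zero

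*SAP*

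**What the plan says.** The SAP's Study design section sets the unit of allocation: "At the start of the study, within each site, nephrologists are randomized to the control or intervention group in a ratio of 1:1". The same section plans eight sites and adds: "Note: two sites were added in 2022, for a total of ten sites".

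Analysis of Primary Outcome gives the size and the error rate: "We aim to recruit 32 nephrologists, each treating on average 10 study patients", and "We desire a two-sided type I error rate of 0.05 and estimate that the between-physician variance is around 10"%. The scale of that 10% is not given. On sites it says: "We plan to use fixed effects to account for clustering by site". On power it says: "we will have a power of 90% to detect a 14.7% increase and a power of 80% to detect a 12.9% increase", from a 10% control rate.

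General Analysis Plan, Primary Outcome, names the test: "The treatment effect will be assessed using a Likelihood Ratio Test (LRT) of the fixed effect from the proportional odds cumulative incidence model". The model has a random physician intercept, fixed site effects and two patient-level covariates. The continuous secondary outcomes (3-9 and 16-19) follow the same pattern: "The treatment effect will be assessed using a LRT of the fixed effect from the linear mixed-effects model". The binary outcomes (2, 10-13) use a logistic mixed model, and outcomes 1 and 14 use the competing-risk model.

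Nowhere does the SAP state maximum likelihood or REML, a reference distribution, denominator degrees of freedom, or resampling for the treatment test. Bootstrapping appears only for the mediation analysis.

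**The concern.** Because whole nephrologists are allocated, the evidence about treatment comes from differences between nephrologists within sites. The number of patients adds precision to each nephrologist's mean but no degrees of freedom for treatment. After the site effects and the treatment effect, only 21 to 29 degrees of freedom remain in the layouts considered below.

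A likelihood ratio test on a fixed effect is by convention a maximum likelihood fit referred to chi-square with 1 df. Maximum likelihood makes no allowance for the 8 to 10 site parameters when it estimates the physician variance, so that variance is biased downward. Chi-square then treats it as known. Both errors make p-values too small.

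At stake is the two-sided 0.05 that the SAP wants for its primary hypothesis, in the same sentence in which it expects physician variance. No level is stated for the secondary outcomes, but their p-values would be too small in the same way.

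**Working it through.** **Inputs from the SAP.** 320 patients (160 per group), 32 nephrologists, 10 patients each, 8 sites (later 10), control rate 10%, two-sided 0.05, physician variance around 10%. **Assumed:** ICCs for the linear outcomes; 32, 40 or 60 nephrologists in ten sites; equal cluster sizes.

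**1. The stated power.** Read the 10% as a logit variance of 0.10:
- Latent ICC = 0.10/(0.10 + 3.29) = 0.0295. Design effect = 1 + 9 x 0.0295 = 1.265. Effective n = 160/1.265 = 126.4 per arm.
- For 10% against 22.9%: SE = sqrt((0.0900 + 0.1766)/126.4) = 0.0459; 0.129/0.0459 = 2.81; power = Phi(2.81 - 1.96) = 80.2%.
- For 10% against 24.7%: SE = 0.0467; 0.147/0.0467 = 3.15; power = 88.2%.

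This is within 2 points of the stated 80% and 90%. An ICC of 0.10 put straight into the design effect (1.9, effective n 84.2) gives only 63.0% and 72.8%. A latent ICC of 0.10 (logit variance 0.366) is not ruled out, however: a simulated logistic likelihood ratio test at that variance has 80-81% power at 12.9 points. The power statement therefore does not settle the scale.

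**2. Degrees of freedom.** Nephrologists - sites - 1: 32 - 8 - 1 = 23; 32 - 10 - 1 = 21; 40 - 10 - 1 = 29.

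**3. Linear outcomes, limit for large ICC.** With K nephrologists the test rejects when K x ln(1 + t²/df) > 3.841, that is when t² > df x (exp(3.841/K) - 1).
- 32/8: t² > 23 x 0.1275 = 2.933, |t| > 1.713, size 10.0%.
- 32/10: t² > 21 x 0.1275 = 2.678, |t| > 1.637, size 11.7%.
- 40/10: t² > 29 x 0.1008 = 2.923, |t| > 1.710, size 9.8%.

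The correct critical values are 2.07, 2.08 and 2.05.

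**4. Linear outcomes, finite ICC.** Treatment, between- and within-nephrologist sums of squares were drawn 400,000 times per setting. The maximum likelihood fit respected the zero-variance boundary and was compared with 3.841.

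| Nephrologists/sites, patients each | ICC 0 | 0.01 | 0.03 | 0.05 | 0.10 |
|---|---|---|---|---|---|
| 32/8, 10 | 5.1% | 6.0% | 7.5% | 8.6% | 9.8% |
| 32/10, 10 | 5.3% | 6.3% | 8.0% | 9.3% | 11.0% |
| 40/10, 8 | 5.3% | 6.1% | 7.2% | 8.2% | 9.4% |

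With 60 nephrologists in ten sites the size is 6.3% at ICC 0.03 and about 7.6% at 0.10. With 32 nephrologists and no site effects it is 4.8-6.0% for ICC 0.01 to 0.20, so the site effects cause most of the excess. With 4-5 responses per nephrologist (assumed for caregiver outcomes) the sizes are 5.9-6.4%, 7.2-8.0% and 8.4-9.7% at ICC 0.01, 0.05 and 0.10.

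**5. Primary outcome, by proxy.** Two proxies were simulated at a 10% rate. One is a quarterly grouped-time proportional odds cumulative incidence model with full 12-month follow-up and death before a consult counted as no consult (4,000 data sets, SE 0.35-0.45 points). The other is a 12-month logistic model (8,000 data sets, SE 0.25-0.31). Both had a physician random intercept and fixed site effects, an assumed site SD of 0.3 on the logit scale, and no patient covariates or attrition.

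| Proxy | Logit variance 0.1 | Latent ICC 0.10 |
|---|---|---|
| Grouped-time, 32/8 | 6.2% | 8.2% |
| Grouped-time, 32/10 | 6.3-6.7% | 8.6-9.1% |
| Grouped-time, 40/10 | 6.4% | 7.5% |
| Logistic, across layouts | 5.8-6.9% | 7.7-8.5% |

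At zero variance the grouped-time proxy gives 5.0% (32/8). A second logistic run (3,000 data sets) gave 6.6% and 7.1% at the lower reading and 8.8% and 9.1% at the higher, for 8 and 10 sites.

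**6. Candidate remedies.**
- Linear, REML with a small-sample F: size 3.1-5.1%.
- Binary, t-test on nephrologist means with (nephrologists - sites - 1) df: 4.6-5.1%.
- F reference on the unchanged ML likelihood ratio test: 4.5-5.4% at logit variance 0.1, but 6.3-7.3% at latent ICC 0.10.
- Re-randomisation, logistic: 3.2-3.8% with ties counted against, 4.6-4.9% with ties broken. Grouped-time: 6.7% on only 600 data sets (SE 1.0), consistent with 5% but too imprecise to confirm it.

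**The case against.** The strongest reply is that maximum likelihood and chi-square are inferred. The SAP states neither, and naming a likelihood ratio test is not in itself an error. That is so, and the figures above are conditional on the usual form. The gap still matters, because the unnamed default does not hold the level that the SAP sets, and otherwise the reference would be left to software or to a choice made after the data are seen.

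Second, the primary model was not itself simulated. This stands. The continuous-time model with covariates and censoring could differ from the proxies by some amount. The linear and logistic mixed models, however, are the SAP's own for most secondary outcomes.

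Third, the layout is uncertain. The eight-by-four plan is offered only as an example, and the number of nephrologists after the two sites were added is not given. This also stands: more than 32 nephrologists would shrink the excess.

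A reader might infer that the primary test runs at 10% or more, double its level. The material does not support that. The highest primary proxy result is 9.1%, at the higher variance reading, and the 9.4-11% figures belong to linear outcomes at an assumed ICC of 0.10. A reader might also infer that re-randomisation is the only sound remedy. It is not: a cluster-level t-test holds its size for binary outcomes and costs about as much power.

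**Conclusion.** The concern holds in its conditional form. The SAP leaves the reference for its treatment test open, and the conventional choice is too liberal for an effect carried by about 32 nephrologists with 8 to 10 site effects. The size is about 6% at ICC 0.01, 7-8% at 0.03 and 9.4-11% at 0.10 for the linear outcomes, where no ICC is given. For the primary it is about 6-7% or about 7-9%, depending on what the 10% means. The primary figures rest on proxies, equal cluster sizes and an assumed site spread. With no physician variance the test is close to 5%. This should be fixed before analysis. At the lower variance reading the excess is modest, one to two points, and it does not undermine the design.

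**What to change.** State the scale of the 10% physician variance, and name the estimation method and reference for every treatment test.

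- **Linear outcomes (3-9, 16-19):** fit by REML and use a Satterthwaite or Kenward-Roger F-test. With near-zero physician variance this is slightly conservative (3.1-4.0%).
- **Primary and the other binary and competing-risk outcomes:** prespecify one test that respects the between-nephrologist degrees of freedom. Either use a re-randomisation test that follows the actual within-site blocked allocation, with the planned model's likelihood ratio as the statistic and a stated tie rule, or a cluster-level t-test on (nephrologists - sites - 1) df. Changing only the reference of the maximum likelihood test to F is not enough at the higher variance reading.
- **Outcome 15:** leave it until its model is settled, since the text names both a logistic and a Cox model.
- **Power:** restate it under the chosen test.

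The cost is some text, programming and power. A plain df correction takes a nominal 80% to 76-77% (noncentrality 2.80: 76.2%, 76.5% and 77.3% at 21, 23 and 29 df). At 12.9 points with 32 nephrologists in 8 sites, re-randomisation gives 78-82% at the lower variance reading, against 87-89% uncorrected. At the higher reading it gives 68-71%, against 80-84% uncorrected. The cluster-level t-test gives about 80% and 70%. Part of each drop is the removed excess size. The stated 80% is roughly kept at the lower reading and not at the higher.

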5. For the **FACT-G total score patient reported health related quality of life** (score range 0-108, 27 items, survey questions 1-27), for each treatment arm, we will report the mean and standard deviation of the **FACT-G total score** at last follow-up (either 2 years of follow-up or last administered survey prior to death, whichever occurs first). The treatment effect will be assessed using a LRT of the fixed effect from the linear mixed-effects model. The linear mixed-effects model will include a random-intercept for physician, and will include fixed effects for: baseline FACT-G score, site, comorbidity, and baseline functional status.

Null Hypothesis: After accounting for baseline differences, there is no difference in the average FACT-G score at last follow-up between control patients and Best Case/Worst Case intervention patients.

Alternative Hypothesis: After accounting for baseline differences, there is a difference in the average FACT-G score at last follow-up between control patients and Best Case/Worst Case intervention patients.

6. For the **FACIT-Pal palliative care subscale (PalS) patient reported health related quality of life** (score range 0-76, 19 items, survey questions 28-46) for each treatment arm, we will report the mean and standard deviation of the subscale composite scores for **PalS** at last follow-up (either 2 years of follow-up or last administered survey prior to death, whichever occurs first). The treatment effect will be assessed using a LRT of the fixed effect from the linear mixed-effects model. The linear mixed-effects model will include a random-intercept for physician, and will include fixed effects for: baseline Pal score, site, comorbidity, and baseline functional status.

Null Hypothesis: After accounting for baseline differences, there is no difference in the average PalS score at last follow-up between control patients and Best Case/Worst Case intervention patients.

Alternative Hypothesis: After accounting for baseline differences, there is a difference in the average PalS score at last follow-up between control patients and Best Case/Worst Case intervention patients.

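### The FACIT-Pal slope model (SAP, secondary outcome 4) omits the baseline FACIT-Pal score; adding it is a free gain in precision and removes sensitivity to chance baseline imbalance

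*SAP*

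**What the plan says.** Under Secondary outcomes in the SAP, item 4 forms one slope per patient. The numerator is the "difference in baseline and either 2 years of follow-up or last administered survey prior to death". The denominator is the time for which that patient was followed. The slope is analysed in a linear mixed model with a random intercept for physician and "fixed effects for: site, comorbidity, and baseline functional status". The null hypothesis begins "After adjusting for baseline differences, there is no difference in the slope of the FACIT-Pal total score".

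The other outcomes that have a baseline score are modelled differently:

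- Item 3 (FACIT-Pal total at last follow-up) has "fixed effects for: baseline FACIT-Pal total score, site, comorbidity, and baseline functional status".
- Item 5 (FACT-G) has "fixed effects for: baseline FACT-G score, site, comorbidity, and baseline functional status".
- Item 6 (palliative care subscale) has "fixed effects for: baseline Pal score, site, comorbidity, and baseline functional status".
- Item 17 (caregiver CAMPAS-R) likewise lists its own baseline score.

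Item 4 is the only one of these five that leaves the baseline score out, and the SAP gives no reason.

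**The concern.** The baseline score is part of the slope, with a negative sign. When baseline and last score are imperfectly correlated, regression to the mean makes the slope negatively related to baseline. An arm that starts lower by chance will then tend to show the better slope with no treatment effect at all. Subtraction does not remove this; a covariate does. Baseline functional status stands in for baseline FACIT-Pal only in part.

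Two things are at stake: precision that could be had for nothing, and a slope contrast that depends on whatever baseline imbalance this randomisation happened to produce. Items 3 and 4 use the same instrument and the same last survey, so they could also disagree merely because one adjusts for baseline and the other does not.

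**Working it through.** The SAP states no SD, correlation, effect size or power for the FACIT-Pal slope, so there is no planned figure to reproduce.

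**Inputs from the SAP.** 160 patients per group; 10% attrition, hence 160 × 0.9 = 144; 80% of patients dying within 2 years; surveys every 3 months for up to 2 years.

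**Assumptions.** SD 25 at baseline and at last survey; baseline-to-last correlation ρ from 0.5 to 0.9; exponential death times; follow-up length t unrelated to score; functional status correlated 0.4 with baseline FACIT-Pal; no physician clustering. The slope is taken as last minus baseline.

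**Step 1, common follow-up t.** The unadjusted slope has variance 2·SD²·(1−ρ)/t². Adding baseline multiplies it by (1+ρ)/2. A baseline gap d shifts the unadjusted contrast by −(1−ρ)·d/t. For d = 5 and t = 1 year:

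- ρ = 0.5: variance cut 25%, shift −2.5 points per year
- ρ = 0.7: 15%, −1.5
- ρ = 0.9: 5%, −0.5

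**Step 2, follow-up that varies because of deaths.** The hazard is ln(5)/2 = 0.805 per year, so 81.8% of patients survive each quarter. About 144 × 0.818 = 118 per arm have a follow-up survey. Among them E[1/t] = 1.552 and E[1/t²] = 3.989, so K = 1.552²/3.989 = 0.604.

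Without functional status in the model:

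- variance cut = (1−ρ)/2 × K
- size of shift = (1−ρ) × 1.552 × 5
- standard error of the unadjusted contrast = √[2 × 2 × 625 × (1−ρ) × 3.989 / 118]

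With functional status kept, as item 4 has it, that covariate already carries 0.4² = 0.16 of the baseline variance. The cut becomes 0.84·(1−ρ)·K / [2 − 0.16·(1−ρ)·K], and the shift is multiplied by 0.84.

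| ρ | Cut, no functional status | Cut, functional status kept | Shift per 5-point gap, no functional status | Standard error | Shift / SE | Shift, functional status kept |
|---|---|---|---|---|---|---|
| 0.5 | 15% | 13% | 3.9 | 6.5 | 0.6 | 3.3 |
| 0.7 | 9% | 8% | 2.3 | 5.0 | 0.5 | 2.0 |
| 0.8 | 6% | 5% | 1.6 | 4.1 | 0.4 | 1.3 |
| 0.9 | 3% | 3% | 0.8 | 2.9 | 0.3 | 0.7 |

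Shifts and standard errors are in points per year. A positive baseline gap gives a negative shift.

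**Step 3, simulation with no true effect.** This used 3,000 runs per scenario, varying follow-up, and functional status in both models. The variance cuts were 13%, 8% and 2% at ρ = 0.5, 0.7 and 0.9. The shift per point of imbalance was −0.68, −0.38 and −0.12 points per year without baseline, so about −3.4, −1.9 and −0.6 for 5 points. With baseline it was within 0.03 of zero. These agree with the formulas to within simulation error.

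**Step 4, type I error.** Over all scenarios, including fixed follow-up and ρ = 0.3, the rejection rate at the nominal 5% level was 0.041 to 0.059 whether or not baseline was included.

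**Step 5, how plausible a 5-point gap is.** With 144 per arm and no clustering, the SD of the gap is 25 × √(2/144) = 2.95. A gap of at least 5 points in either direction then has probability about 9%. If the SAP's figure of around 10% for between-physician variance is read as an intraclass correlation and carried over to FACIT-Pal (an assumption), with 144/16 = 9 patients per physician, the variance of the gap is multiplied by 1 + 8 × 0.1 = 1.8 and the probability is about 20%.

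**The case against.** **Is it a fault at all?** Items 3, 5, 6 and 17 analyse a level, where baseline can enter only as a covariate. Item 4 analyses a change, where baseline already enters by subtraction. Such an analysis is valid under randomisation, and item 3 already supplies a baseline-adjusted result on the same instrument. The validity point stands. But item 3 does not repair item 4's own test, and subtraction is the less efficient use of baseline throughout the range examined.

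**Does item 4 break its own promise?** A reader might infer that the hypothesis wording commits the model to adjusting for baseline FACIT-Pal. The SAP does not support this. Near-identical wording introduces almost every hypothesis, including those for palliative care receipt and ICU admission, which have no baseline value of the outcome. It can mean just the listed covariates. The better evidence is the contrast with the sister models.

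**Is the error rate inflated?** A reader might infer this too. It is not: averaged over randomisations, the unadjusted test holds its level. The bias is conditional on the imbalance observed.

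**Is the omission the main source of noise?** No. Under the same assumptions, patients last surveyed at 3 months are 18% of those analysed and supply about 73% of the slope variance. That comes from dividing by short follow-up, and the covariate leaves it essentially unchanged.

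**Would one baseline coefficient be misspecified?** Yes, because regression to the mean scales with 1/t. The varying-follow-up simulation contained that misspecification, and adjustment still did not increase the variance.

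**Conclusion.** The point holds as a free improvement to one secondary analysis. Item 4 omits a covariate that the plan uses for every comparable outcome. With functional status kept, adding it would cut residual variance by about 13% at a correlation of 0.5 and about 3% at 0.9. It would also remove a shift that, for a 5-point chance gap, is about 3.9 to 0.8 points per year without functional status (0.6 to 0.3 standard errors) and somewhat smaller with it. A gap of that size is plausible, not certain.

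These sizes rest on the assumed SD, correlation and death-time distribution, none of which the SAP gives for this outcome. At high correlation the gain is small. The validity of the test and the primary outcome are not in question.

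**What to change.** Add the baseline FACIT-Pal total score to the fixed effects of item 4, as in item 3, or state why it is left out. The score is already needed to compute the slope and to fit item 3, so the cost is one phrase in the SAP and one degree of freedom.

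A single mixed model on all quarterly scores, with patient-level random intercept and slope, would also give less weight to short follow-up. That is a separate, optional proposal, and this point does not depend on it.
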